### **Objectives**

Primary:

- to determine the efficacy of nivolumab as therapy for MF

Secondary:

- to determine the safety of nivolumab as therapy for patients with MF

Exploratory:

- to explore time to response and duration of response
- to assess changes in symptom burden
- to explore changes in bone marrow fibrosis
- to explore changes in JAK2V617F (or other molecular marker) allele burden or changes in cytogenetic abnormalities

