## **5.0 TREATMENT PLAN**

On this study 4 weeks of therapy is considered one cycle of therapy. Nivolumab will be given IV in outpatient setting at 3 mg/kg approximately every 2 weeks (every 14 days +/- 2 days; patients may be dosed no less than 12 days from the previous dose of drug) for 8 doses followed by a maintenance regimen of one dose every 12 weeks. Nivolumab should be administered as an IV infusion over 60 minutes through an intravenous line containing a sterile, nonpyrogenic in-line filter (0.2- to 1.2-micron, low-protein binding polyethersulfone membrane). Patients experiencing clinical benefit will continue therapy for 4 years unless progression of disease or toxicity warranting discontinuation of therapy is observed.

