### **5.5 Discontinuation Criteria**

Treatment should be permanently discontinued for the following study drug related events:

- Any life-threatening or Grade 4 adverse reaction
- Grade 3 or 4 pneumonitis
- Grade 4 colitis
- AST or ALT greater than 5 times ULN or direct bilirubin greater than 3 times ULN
- Creatinine greater than 6 times ULN
- Any severe or Grade 3 treatment-related adverse reaction that recurs
- Inability to reduce corticosteroid dose to 10 mg or less of prednisone or equivalent per day within 12 weeks
- Persistent Grade 2 or 3 treatment-related adverse reactions that do not recover to Grade 1 or resolve within 12 weeks after last dose of therapy
- Any dosing interruption lasting > 6 weeks with the following exceptions:
  - Dosing interruptions > 6 weeks but not exceeding 12 weeks to allow for prolonged steroid tapers to manage drug-related adverse events are allowed. Prior to re-initiating treatment in a subject with a dosing interruption lasting > 6 weeks, the Principal Investigator must be consulted. Tumor assessments should continue as per protocol even if dosing is interrupted
  - Dosing interruptions > 6 weeks that occur for non-drug-related reasons may be allowed if approved by the Principal Investigator. Prior to re-initiating treatment in a subject with a dosing interruption lasting > 6 weeks, the Principal Investigator must be consulted. Tumor assessments should continue as per protocol even if dosing is interrupted
- Any adverse event, laboratory abnormality, or intercurrent illness which, in the judgment of the Investigator, presents a substantial clinical risk to the subject with continued nivolumab dosing

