## 5.6 Evaluation During Study

- Directed history and physical examination including vital signs, body weight, and spleen and liver measurements on Days 1, 7, and 14 of Cycle 1, then on Day 1 and Day 14 (+/- 2 days) of Cycles 2 – 4, then on Day 1 of Cycle 5, and then on Day 1 (+/- 7 days) of every 3rd cycle after that (Cycles 8, 11, 14 and so on). This also includes a transfusion history and concomitant medication notation.
- CBC and differential, electrolytes (Na, K, Cl, HCO3), creatinine, BUN, glucose, total bilirubin, SGOT and SGPT, amylase and lipase on Days 1, 7, and 14 of Cycle 1, then on Day 1 and Day 14 of Cycles 2 – 4 (+/- 2 days), then on Day 1 of Cycle 5, and then on Day 1 (+/- 7 days) of every 3rd cycle after that (Cycles 8, 11, 14 and so on).
- Bone marrow aspiration and biopsy after 4 cycles, and if deemed appropriate by the investigator, then every 12 weeks.
- Response assessment after 4 cycles of therapy, then every 12 weeks
- Pregnancy test after 2 and 4 cycles of therapy, then every 12 weeks
- Continuous assessment of AEs
- MPN-SAF TSS questionnaire on Day 1 and Day 14 (+/- 2 days), of cycles 1-4, then on Day 1 of Cycle 5 (+/- 7 days), then Day 1 (+/- 7 days) of every 3rd cycle after that.

Every effort will be made to adhere to the schedule of events and all protocol requirements. Variations in schedule of events and other protocol requirements that do not affect the rights and safety of the patient will not be considered as deviations. Such variations may include laboratory and history and physical exam assessments completed outside of schedule, occasional missed required research samples.

The patient will be contacted by the PI and his staff approximately 30, 60 and 100 days after discontinuation of study drug to assess for AE's, unless the patient receives further MF-directed treatment. Pregnancy test (for FCBP only) will be required approximately 30, 60 and 100 days after discontinuation of study drug.

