**Table 8.b. Operating characteristics for toxicity monitoring**

True toxicity rate	Prob(stop the trial early)	Average sample size
0.1	0.0006	40
0.2	0.021	39
0.3	0.186	36
0.4	0.583	27
0.5	0.905	17

Summary statistics will be provided for continuous variables. Frequency tables will be used to summarize categorical variables. The objective response rate (ORR) will be estimated along with the exact 95% confidence interval. Data from all subjects who receive any study drug will be included in the safety analyses. The severity of the toxicities will be graded according to the NCI CTCAE v4.03 whenever possible. We will follow standard reporting guidelines for adverse

events. Safety data will be summarized by category, severity and frequency. The proportion of patients with AEs will be estimated, along with the Bayesian 95% credible intervals.

**Duration of response:** Duration of response is defined as the date at which the subject's objective status is first noted to be a CR, PR or CI to the date of progression (no longer meeting criteria for either CR, PR or CI) is documented (if one has occurred). Patients who continue to respond as of the data cut-off date will be censored as of the date of their last assessment documenting continued response.

**Time to response:** The time to response is defined as the time from study registration to the first date at which the subject's objective status was classified as a response (CR, PR or CI). In subjects who do not achieve a response, time to response will be censored at the subject's last evaluation date.

The distribution for each of these event-time variables (duration of response and time to response) will be estimated by Kaplan-Meier curves.

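### Exploratory time to response: Kaplan-Meier with every non-responder censored overstates the proportion responding when patients die, progress or stop for toxicity or lack of effect before a later response (minor)

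*Combined protocol and SAP*

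**What the plan says.** The Objectives list both endpoints as exploratory: "to explore time to response and duration of response". Section 9.0 runs time to response from registration to the first CR, PR or CI. For everyone else, "In subjects who do not achieve a response, time to response will be censored at the subject's last evaluation date". The estimator follows: "The distribution for each of these event-time variables (duration of response and time to response) will be estimated by Kaplan-Meier curves". Section 9.0 names no competing-risk method.

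Duration of response runs from first response "to the date of progression (no longer meeting criteria for either CR, PR or CI) is documented". Its one censoring rule is "Patients who continue to respond as of the data cut-off date will be censored", at the last assessment that shows continued response.

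Other sections determine who leaves early:

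- Section 5.0 continues treatment in patients with benefit "unless progression of disease or toxicity warranting discontinuation of therapy is observed".
- Section 5.5 (Discontinuation Criteria) opens its list with "Treatment should be permanently discontinued for the following study drug related events".
- Section 5.7 (Criteria for Removal from the Study) adds lack of effect, withdrawal of consent, loss to follow-up and death.
- Section 5.6 (Evaluation During Study) schedules "Response assessment after 4 cycles of therapy, then every 12 weeks". After the drug is stopped it lists adverse-event contacts and pregnancy tests at about 30, 60 and 100 days, and no response assessment.
- Section 6.0 requires benefit to last 12 weeks before it counts as a response.

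**The concern.** Kaplan-Meier assumes that a censored patient has the same future chance of the event as those still followed. That is reasonable for a patient cut off by the calendar. It cannot hold for one who has died. It is doubtful for one who progressed or was taken off for toxicity or lack of effect, because those exits are tied to outcome and the schedule then ends response assessment. The estimator removes these patients from the denominator and in effect assigns them later responses that nobody observed.

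First responses remain possible at assessments after cycle 4, so exits can precede responses. The report could then show a time-to-response curve whose height is read as the proportion responding, when it is higher than that proportion.

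The duration endpoint has a smaller gap. Death after at least 12 weeks of benefit is neither a named event nor clearly covered by the censoring rule, so two analysts could draw different curves from the same data.

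**Working it through.** The plan gives no figure for either endpoint, so there is none to reproduce.

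**Inputs from the documents.** Maximum N = 40 and a final success threshold of 11 responders (Section 9.0); target ORR 35%, that is 14/40. A cycle is 4 weeks (Section 5.0), so assessments fall at 4 × 4 = week 16, then about weeks 28 and 40 (Section 5.6, Evaluation During Study).

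**Assumed inputs.** The number and timing of exits, and the split of responses across assessments.

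**Formulas.** Kaplan-Meier proportion = 1 − Π(1 − d/n), where d is responses and n is patients still at risk at each assessment. Aalen-Johansen cumulative incidence = Σ S(t−) × d/n, where S(t−) is the probability of having had neither a response nor a competing event just before that assessment.

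**Example 1.** 11 responses at week 16, 2 more at week 28 (13/40 = 32.5%), and k exits between the two. After week 16, 29 patients remain, so KM = 1 − (29/40) × (1 − 2/(29 − k)).

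| k | KM at week 28 |
|---|---|
| 0 | 32.5% |
| 2 | 32.9% |
| 5 | 33.5% |
| 10 | 35.1% |
| 15 | 37.9% |

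**Example 2.** 14 responders (35%): 8, 4 and 2 at weeks 16, 28 and 40.

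- 9 exits (2 before week 16, 4 in weeks 16–28, 3 in weeks 28–40): 1 − (30/38)(22/26)(17/19) = 40.2%.
- 18 exits (4, 8 and 6 in the same intervals): 1 − (28/36)(16/20)(8/10) = 50.2%.
- No early exits: 35.0%.
- All 14 responses at week 16 and all exits later: 35.0%.

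With every exit counted as a competing event and no other early censoring, cumulative incidence is 14/40 = 35.0% in all four cases.

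**How exits are classed decides the answer.** Take Example 1 with k = 10 and apply Aalen-Johansen:

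- All 10 competing: 11/40 + (19/40)(2/19) = 32.5%.
- 7 competing, then 3 censored: 11/40 + (22/40)(2/19) = 33.3%.
- 3 censored, then 7 competing: 11/40 + (29/40)(19/26)(2/19) = 33.1%.
- All 10 censored: 11/40 + (29/40)(2/19) = 35.1%, the Kaplan-Meier value.

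Naming the estimator is therefore not enough; the competing events must be named too.

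**Duration.** Assume 11 responders, 2 deaths after at least 12 weeks of benefit, then 3 losses of response. With deaths censored, 1 − 3/9 = 66.7% are still in response. With deaths as events, 6/11 = 54.5%.

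**The case against.** **No decision depends on this.** Both endpoints are exploratory and carry no test or threshold. This stands, and it is why the point is minor. A reader might infer that the efficacy conclusion is inflated. The documents do not support that: the primary ORR is a binomial proportion after 4 cycles with an exact confidence interval, and the 4/16 and 11/40 rules count responders directly.

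**A curve above responders divided by patients treated is not in itself an error.** This also stands. At 1–2 patients a month, 40 patients take 20 to 40 months to accrue. An analysis before all have reached the later assessments would censor some of them properly, and there the crude fraction is the one that is too low. The defect is confined to exits that end or alter the chance of response.

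**Kaplan-Meier has a meaning of its own.** If exits were unrelated to response, it would estimate the proportion who would have responded had nobody left. That is a coherent quantity, but Section 9.0 does not say it is wanted, and exits for progression or lack of effect are unlikely to be unrelated to response.

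**The sizes are assumed.** They are. The 15-exit case needs 15 of 29 remaining non-responders to leave within 12 weeks. The 5.4-point gap there (37.9 − 32.5) might be read as a ceiling, but Example 2 gives 5.2 and 15.2 points under other assumptions. Comparing the gap with a confidence interval does not settle it either, because this is a difference in what is estimated and not sampling error.

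**Conclusion.** The concern holds as a minor point on exploratory reporting. Followed as written, the time-to-response curve overstates the proportion actually responding whenever death, progression, or discontinuation for toxicity or lack of effect without response precedes someone else's later response. The direction follows from the estimator. The size depends on exits that the documents do not quantify: 0 to 5.4 points in the first set of scenarios, and 5.2 or 15.2 points in the second with 9 or 18 exits. If no such exit precedes a later response, there is no excess.

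The missing rule for death in response is a secondary wording gap. It concerns deaths after 12 weeks of benefit. Under Section 6.0 an earlier death leaves the patient a non-responder, who is then censored in time to response. It would be too strong to say that the plan wrongly censors deaths in response, because it does not say what happens to them.

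**What to change.** **Time to response.** Report cumulative incidence (Aalen-Johansen). Name as competing events death, progression, and permanent discontinuation for toxicity or lack of effect, each without prior response. Censor only at data cut-off, withdrawal of consent and loss to follow-up.

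A simpler alternative is the median and range among responders. State that it counts first responses at any time, so it may include more patients than the ORR after 4 cycles (in Example 1, 13 against 11).

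The cost is SAP wording, standard software and a slightly less favourable curve.

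**Duration of response.** Count death in response as an event, as far as survival status is recorded, and state how responders who start other myelofibrosis treatment are handled. Section 7.2 captures serious adverse events, including deaths, to 100 days after the last dose unless consent is withdrawn. The contacts in Section 5.6 (Evaluation During Study) end at about 100 days, or when further myelofibrosis treatment begins. Counting later deaths would need survival status to be collected, which is a data cost beyond wording.

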## APPENDIX 1     SAMPLE OF DRUG ORDERING     AND PHARMACY REFERENCE MATERIAL

### Nivolumab (BMS-936558) Pharmacy Reference Material

- Nivolumab has a concentration of 10mg/mL and is provided in a 10mL vial. Ten or five vials are provided in a carton.

#### ***Initial Orders***

- *Following submission and approval of the required regulatory documents, a supply of nivolumab may be ordered from BMS by completing a Drug Request Form provided by BMS for this specific trial. The first request may take place upon screening of the first patient*
- *The initial order should be limited to 20 vials. Allow 5 business days for shipment of drug from BMS receipt of the Drug Request Form. Drug is protocol specific, but not patient specific. All drug product will be shipped by courier in a temperature-controlled container. It is possible that sites may have more than one nivolumab clinical study ongoing at the same time. It is imperative that only drug product designated for this protocol number be used for this study.*
- Pharmacy supplies not provided by BMS: Empty IV bags/containers, approved diluents, In-line filters and infusion tubing

#### ***Re-Supply***

- *Drug re-supply request form should be submitted electronically business days before the expected delivery date. Deliveries will be made Tuesday through Friday.*
- *When assessing need for resupply, institutions should keep in mind the number of vials used per treatment dose, and that shipments may take 14 business days from receipt of request. Drug is not patient-specific. Be sure to check with your pharmacy regarding existing investigational stock to assure optimal use of drug on hand.*

#### ***Drug Excursions***

- *Drug excursions should be reported immediately to BMS on the form provided with the study-specific drug order form*

***Please refer to the most recent version of the Investigator Brochure for additional information.***

#### **Storage Conditions & Handling:**

- Store at 2-8°C (36-46°F), protect from light, freezing, and shaking.
- If any temperature excursions are encountered during storage, please report these to BMS for assessment via the Temperature Excursion Response Form.

- As with all injectable drugs, care should be taken when handling and preparing nivolumab. Whenever possible, nivolumab should be prepared in a laminar flow hood or safety cabinet using standard precautions for the safe handling of intravenous agents applying aseptic technique.
- Partially used vials should be disposed at the site following procedures for the disposal of anticancer drugs.

After final drug reconciliation, unused nivolumab vials should be disposed at the site following procedures for the disposal of anticancer drugs. For further information, please either discuss with your BMS CSR&O protocol manager or refer to your site IP Destruction policies and procedures

**Use Time/Stability:** Please refer to section 3.2.3 of the current Investigator's Brochure. The time of preparation should be noted in the Pharmacy Source documents [accountability logs] or in study files as required for investigator sponsored research [FDA and GCP]

The administration of nivolumab infusion must be completed within 24 hours of preparation. If not used immediately, the infusion solution may be stored under refrigeration conditions (2°-8°C, 36-46°F) for up to 24 hours; and a maximum of 4 hours of the total 24 hours can be a room temperature (20°-25°C, 68°-77°F) and room light. The maximum 4-hour period under room temperature and room light conditions includes the product administration period.

#### **Preparation and Administration:**

1. Visually inspect the drug product solution for particulate matter and discoloration prior to administration. Discard if solution is cloudy, if there is pronounced discoloration (solution may have a pale-yellow color), or if there is foreign particulate matter other than a few translucent-to-white, amorphous particles.  
*Note: Mix by **gently** inverting several times. **Do not** shake.*
2. Aseptically withdraw the required volume of nivolumab solution into a syringe, and dispense into an IV. bag. If multiple vials are needed for a subject, it is important to use a separate sterile syringe and needle for each vial to prevent problems such as dulling of needle tip, stopper coring, repeated friction of plunger against syringe barrel wall. **Do not** enter into each vial more than once. **Do not** administer study drug as an IV push or bolus injection
3. Add the appropriate volume of 0.9% Sodium Chloride Injection solution or 5% Dextrose Injection solution. *It is acceptable to add nivolumab solution from the vials into an appropriate pre-filled bag of diluent.*

**Note: Nivolumab infusion concentration must be at or above the minimum allowable concentration of 1 mg/mL.**

**Note: It is not recommended that so-called "channel" or tube systems are used to transport prepared infusions of nivolumab.**

4. Attach the IV bag containing the nivolumab solution to the infusion set and filter. Nivolumab should be administered as an IV infusion over 60 minutes through an intravenous line containing a sterile, nonpyrogenic in-line filter (0.2- to 1.2-micron, low-protein binding polyethersulfone membrane).
5. At the end of the infusion period, flush the line with a sufficient quantity of approved diluents.

**Example Dose Calculation [at 3mg/kg]:**

**Total dose should be calculated as follows (assuming total dose volume of 210 mL, 70 kg pt, dose of 3 mg/kg):**

- Subject body weight in kg x 3 mg (for the 3 mg/kg cohort) = total dose (mg)  
 $70 \text{ kg} \times 3 \text{ mg/kg} = 210 \text{ mg}$
- Total dose (mg)  $\div$  10 mg/mL = Amount of solution to be withdrawn from vials  
 $210 \text{ mg} \div 10 \text{ mg/mL} = 21 \text{ mL}$

**Example of Total volume of solution to infuse (mL) for a minimum conc solution. –  
Volume of 10 mg/mL solution (mL) = Volume of Diluent (mL) to add**

$$210 \text{ mL} - 21 \text{ mL} = 189 \text{ mL}$$

Please note it is perfectly acceptable to dose Nivolumab at a higher drug concentrations, **as long as the total volume of diluted solution is at or above the minimum allowable concentration of 1 mg/mL, below is the calculation based on the above example. Please double check.**

Total dose in mg  $\div$  Total volume to infuse in mL = Overall drug concentration, mg/mL

$$210 \text{ mg} \div 210 \text{ mL} = 1 \text{ mg/mL}$$
